2.3. Benefit-Risk Assessment

More detailed information about the known and expected benefits and risks and reasonably expected adverse events (AEs) of LY900014 may be found in the IB.

2.3.1. Risk Assessment

Potential Risk of Clinical Significance	Summary of Data/Rationale for Risk	Mitigation Strategy
Study Intervention (s) LY900014		
Hypoglycemia Hyperglycemia Hypersensitivity and Allergic reactions	See IB Section 6.2.2.5.1	Each participant will receive Diabetes education and counseling on how to avoid the risks of hypoglycemia and hyperglycemia at Visit 2. CGM alerts will be set up during Visit 2 for early detection of hypoglycemia and hyperglycemia. Participants with known hypersensitivity or allergy to any of the study medications or their excipients will be excluded from the study.
Study Procedures		
InPen and Mobile medical app (MMA)		
Errors of LY900014 dose delivery	
LY900014 is not approved to be used with InPen; however, it is expected to perform similarly to Humalog due to the following reasons:
 
 • InPen is compatible with Humalog U-100 3.0 mL cartridges, which have the same dimensions to LY900014 cartridges • Lilly has internal data for LY900014 supporting in use stability for the container closure and fluid path (that is, needle), which are the same as Humalog • LY900014 and Humalog are shown to be equipotent in clinical pharmacology studies • LY900014 and Humalog substituted generally on a unit-for-unit basis in clinical pharmacology and Phase 3 studies • In the pivotal study of LY900014 in adult patients with T1D, Study ITRM, at study endpoint of 26 weeks, doses of LY900014 and Humalog were not significantly different after titration • There were no meaningful difference in safety observed between LY900014 and Humalog in Phase 3 studies (that is, incidence of adverse events and 	
 • Lilly has completed preliminary testing of InPen supporting dose accuracy when used with LY900014. Definitive dose accuracy testing will be completed before study initiation • Real-time CGM guided insulin titration with hypo- and hyperglycemia alerts set up • Site selection: choose experienced primary investigators (PIs) and site staff with LY900014 and diabetes technology • Strict monitoring of patients through frequent interactions with investigators, who have 24/7 access to patient CGM data in CLARITY • Enrollment of technologically-competent and highly compliant patients • Carefully planned site training and patient training 
Based on the medical risk assessment, potential risks of using InPen with LY900014 off-label can be managed effectively upon the implementation of risk mitigation

Potential Risk of Clinical Significance	Summary of Data/Rationale for Risk	Mitigation Strategy
	
hypoglycemia)
 
 • There were no clinically meaningful difference between LY900014 and Humalog in pump settings or bolus calculator settings (including active insulin time) in Phase 3 studies 	
plans. Lilly Medical concluded that if InPen passes Lilly dose accuracy testing with LY900014, InPen can be safely used in Study ITSZ due to the expected similar performance between LY900014 and Humalog

Abbreviations: CGM = continuous glucose monitoring; T1D = type 1 diabetes.

2.3.2. Benefit Assessment

No direct clinical benefit is anticipated from participating in this trial due to the short nature of this study. However, some participants may benefit from improved glycemic control as a result of the dose titration strategy, frequent ICR, ISF, DIA, and insulin dose adjustments, and increased engagement with an HCP.

More detailed information about the known and expected benefits and risks of LY900014 along with its clinical and nonclinical development can be found in the IB.

More detailed information about the known and expected benefits and risks of degludec may be found in the USPI (Tresiba package insert, 2015).

2.3.3. Overall Benefit: Risk Conclusion

Considering the measures taken to minimize risk to participants involved in this study, the potential risks identified in association with LY900014 are justified by the potential benefits that may be afforded to participants with T1D.

3. Objectives and Endpoints

Objectives	Endpoints
Primary	
To evaluate the time that glucose values are within the target range 70 to 180 mg/dL from CGM use, after 35 days of using the study titration scheme with LY900014 treatment and degludec	Percentage of time with sensor glucose values between 70 and 180 mg/dL (both inclusive), with CGM use during the maintenance period
Secondary	
To evaluate ICR with LY900014 treatment	ICR at the end of the maintenance period
To evaluate the relationship between ICR and TDD with LY900014 treatment	ICR×TDD for the maintenance period
To evaluate total daily, basal, and prandial insulin dose with LY900014 treatment and degludec	Prandial: TDD ratio for the maintenance period
Tertiary/Exploratory	
To evaluate the safety of LY900014	Adverse events and vital signs
To explore the relationship between 
 • ICR and TDD • ISF and TDD • ICR and ISF with LY900014 treatment	
 • Slope of the linear regression line of ICR or ISF on the reciprocal of TDD • Slope of the linear regression line of ICR on ISF, for the maintenance period
To explore ISF with LY900014 treatment	ISF at the end of the maintenance period
To explore glucose profiles, obtained from CGM use with LY900014 treatment	Actual and change from baseline in mean sensor glucose with CGM use during the maintenance period
To explore highest PPG level within 4 hours* after meal(s), obtained from CGM use, with LY900014 treatment	Actual and change from baseline in highest PPG level within 4 hours after meal(s), with CGM use during the maintenance period

Objectives	Endpoints
To explore the time from start of meal to highest PPG level within 4 hours* after meal(s), obtained from CGM use, with LY900014 treatment	Actual and change from baseline in minutes from start of meal to highest PPG level within 4 hours after meal(s), with CGM use during the maintenance period
To explore the percentage of time spent in hypoglycemic glucose ranges, obtained from CGM use, with LY900014 treatment	Actual and change from baseline in percentage of time with sensor glucose values <54 mg/dL, with CGM use during the maintenance period
To explore percentage of time spent in hyperglycemic glucose ranges, obtained from CGM use, with LY900014 treatment	Actual and change from baseline in percentage of time with sensor glucose values >250 mg/dL, with CGM use during the maintenance period
To explore within-day glucose variability, obtained from CGM use, with LY900014 treatment	Actual and change from baseline in within-day CV of sensor glucose, with CGM use during the maintenance period
To explore proportion of participants achieving CGM-based glycemic targets, with LY900014 treatment	
The proportion of participants with percentage of time in
 
 • target glucose range, 70-180 mg/dL, >70% • hypoglycemia, <54 mg/dL, <1% • hyperglycemia, >250 mg/dL, <5%, 
with CGM use during the maintenance period

To explore fructosamine with LY900014 treatment	Fructosamine at the end of the maintenance period compared to baseline
To explore HbA1c with LY900014 treatment	HbA1c at the end of the maintenance period compared to baseline
To explore 1,5 Anhydroglucitol (AG) with LY900014 treatment	1,5 AG at the end of the maintenance period compared to baseline

Abbreviations: CGM = continuous glucose monitoring; CV = cardiovascular; HbA1c = hemoglobin A1c; ICR = insulin-to-carbohydrate ratio; ISF = insulin sensitivity factor; PPG = post-prandial glucose; TDD = Total Daily Dose.

* Excluding the glucose data from participants who have had the next meal event before the end of time interval.

4. Study Design

4.1. Overall Design

Study ITSZ is a multicenter, single-group, open-label, Phase 2, exploratory study that will be conducted in participants with T1D currently treated with insulin degludec and a rapid-acting insulin analog in an MDI regimen. The objective of the study is to assess the percentage of time glucose values are within the target range of 70 to 180 mg/dL after 35 days of titration using the study titration scheme.

The study will consist of the following periods:

- Screening and lead-in period
- Treatment period
 - Titration period
 - Maintenance period
- Safety follow-up period

4.1.1. Study Visits

Screening, Visit 1

The purpose of procedures at the screening visit is to establish eligibility for the study (see Sections 5.1 and 5.2). Participants will continue their pre-study rapid-acting insulin analog and their basal insulin dose. Insulin-to-carbohydrate ratio, insulin sensitivity factor (ISF), and DIA should not be changed unless for safety reasons during the screening period.

Lead-in Period, Visit 2

The lead-in period starts following Visit 2. During the lead-in period, all participants will administer Humalog as rapid-acting insulin with the InPen Pen Injector. Participants who enter the study on Novolog, Admelog, or Apidra will transition to Humalog at Visit 2. The dose of insulin degludec and the ICR, ISF, and DIA should not be changed unless for safety reasons.

Sponsor Provided CGM Session

At Visit 2, Dexcom G6 CGM sensors and transmitter will be dispensed to all participants who meet study entry criteria.

All participants will switch to a Lilly provided Dexcom G6 CGM system during Visit 2. Also, any participant using a personal Dexcom G6 will switch to a Lilly provided Dexcom G6 during Visit 2. All participants will use Dexcom G6 CGM from Visit 2 until Visit 14. Participants will grant permission to the site to access their CGM data.

At Visit 2, participants will insert a new Lilly provided sensor and transmitter. Between Day -11 and Day 46, participants will wear the study-provided G6 CGM system and change the sensor every 10 days or as needed. All participants should use the sensor code printed on the back of the adhesive patch to calibrate when starting a new sensor. Calibrating Dexcom G6 CGM using fingerstick meter values is prohibited in this study to avoid increased sensor measurement variability across participants caused by using different brands/models of glucose meters for calibration.

All participants will use the Dexcom mobile app on their smart phone to view their CGM data during the study. Participants who enter the study using Dexcom G6 CGM will not use their Dexcom G6 CGM receiver to view CGM data.

Sites will work with the participant to ensure:

- the Dexcom CGM mobile app is installed on the participant's smart phone
- participant has an active Dexcom mobile app business account
- CGM device and associated Mobile medical app (MMA) is set up so that
 - all alerts and notifications are enabled
 - alert levels are adjusted, if necessary
 - location services are enabled
- participant grants permission to the site to view his or her CGM data through CLARITY and SMS

During the lead-in period from Day -10 to Day -1, participants are required to enter the following data into the Dexcom mobile app every day:

- meal start time for breakfast, lunch, and dinner
- insulin degludec dose

Investigator staff should check CLARITY to ensure that participants are entering these data during the lead-in period.

Training related to the use of Dexcom G6 CGM and its associated mobile app will be provided at Visit 2. Abbreviated training following Visit 2 will be made available as deemed appropriate.

Minimum CGM Requirements

The CGM data collected during the lead-in period will be used as baseline CGM. Participants must have at least 5 days with a minimum of 70% CGM measures per day during the lead-in period to be eligible for treatment assignment. These 5 days do not need to be consecutive.

The investigator will have daily access to the SMS portal during the lead-in period and will print the participant's Data Acceptability Report to determine the participant's eligibility for treatment assignment. The investigator should determine before Visit 3 that the participant has met the minimum CGM eligibility requirements and then communicate to the participant their eligibility for treatment assignment. If the investigator becomes aware through SMS portal monitoring during the lead-in period that a participant will not meet the minimum CGM requirements before Visit 3, the site should advise the participant to re-schedule Visit 3 to a later date within the visit window.

InPen

During Visit 2, InPen Pen Injector and associated supplies will be dispensed to all participants who meet study entry criteria. The InPen mobile app will be downloaded onto the participants' smartphone.

Sites will work with the participant to ensure:

- InPen mobile app is installed on the participant's smart phone
- participant has an active InPen mobile app business account

- Participants have entered the following information in the InPen device and associated MMA:
 - Target blood glucose: this is the blood glucose value the participant is trying to achieve. It is prescribed by investigators and individualized for each participant in the study. The target blood glucose will be used by the dose calculator to calculate the correction bolus and is distinct from the glycemic targets used for insulin titration defined in Section 4.3.
 - ICR
 - ISF
 - DIA

Participants are required to enter meal or snack carbohydrates and current CGM glucose before each meal/snack into the InPen mobile app in order to use the bolus dose calculator during the study.

Training related to the use of InPen Reusable Pen Injector and its associated mobile app will be provided at Visit 2. Abbreviated training following Visit 2 will be made available as deemed appropriate.

Transcribing Data into the eCRF at Visit 2

At Visit 2, the investigator should transcribe the following data from the day before the visit into the eCRF:

- ICR
- ISF
- DIA

Diabetes Education

Initial training related to diabetes education and nutrition counseling will be provided at Visit 2 and other visits as needed. Appropriate site personnel will administer education using locally approved diabetes education materials and programs or by using other materials that may be provided by the Sponsor.

Treatment Period, Visit 3 to Visit 14

Treatment Assignment, Visit 3 (Day 0)

The investigator should determine eligibility for treatment assignment before Visit 3. There will be no early enrollment if a participant meets the minimum 5-day requirement of 70% CGM readings per day before Visit 3.

For participants who are eligible for treatment assignment, Humalog will be discontinued, and LY900014 will be initiated using their current ICR, ISF, and DIA at Visit 3. All participants who are not currently administering insulin degludec in the morning should switch to morning administration with the investigator's guidance. All participants should continue administering degludec in the morning throughout the treatment period.

Titration Period, Visit 3 through Visit 13 (Day 0 to Day 35)

Following treatment assignment at Visit 3, participants will enter a 35-day insulin titration period. The investigator may adjust the dose of insulin degludec, ICR, ISF, or DIA at any time from Visit 3 (Day 0) to Visit 13 (Day 35) to meet the glucose targets specified in Section 4.3.1.

Participant's ambulatory glucose profile will be reviewed using CGM data from CLARITY at each visit.

Participant's LY900014 dose will be reviewed using the InPen report. The investigator should confirm that the InPen report has been received before each study visit. Additionally, the investigator should confirm that the InPen report aligns with the clinical management of the participant. Based on these reports, insulin doses, ICR, ISF, and DIA will be adjusted as needed to reach the study specified glucose target (Sections 4.3.1 and 4.3.2).

Maintenance Period, Day 36 to Day 46

The maintenance period starts following Visit 13. Continuous glucose monitoring data collected during the maintenance period will be used as endpoint CGM data.

During the maintenance period, the investigator may not adjust the dose of insulin degludec, ICR, ISF, or DIA unless for safety reasons.

During the maintenance period from Day 36 to Day 45, participants are required every day to enter the following data into the Dexcom mobile app

- meal start time for breakfast, lunch, and dinner
- insulin degludec dose

Investigator staff should check CLARITY to ensure that participants are entering these data during the maintenance period.

Visit 14 (Day 46)

At Visit 14, participants will return to their non-study rapid-acting insulin analog regimen. Participants may decide to continue to administer degludec in the morning or switch to their pre-study dosing schedule. The investigator will determine basal and prandial insulin doses.

At Visit 14, participants will return to the personal CGM system that they were using before the study began. Participants should be reminded before Visit 14 that they will need to bring their personal CGM system to Visit 14.

Transcribing Data into the eCRF from Visit 3 to Visit 14

At every visit from Visit 3 to Visit 14 inclusive, the investigator should transcribe the following data from the day before the visit into the eCRF:

- ICR
- ISF
- DIA

Transcribing Data into the eCRF for Visit 3 and Visit 14 only

In addition to the ICR, ISF, and DIA, the investigator should transcribe the Humalog dose at Visit 3 (data from Day -10 to Day -1) and the LY900014 dose at Visit 14 (data from Day 36 to Day 45).

Safety Follow-up, Visit 801

All randomized participants who completed the treatment period should have a safety follow-up visit approximately 1 week after Visit 14.

Early Termination visit, ET Visit

Participants who discontinue investigational product (IP) permanently before completion of the treatment period for any reason will also be discontinued from the study. An (ET) visit should be conducted as soon as reasonably possible. After the ET visit, a safety follow-up assessment (Visit 801) should be conducted approximately 1 week after the ET Visit.

Transcribing Data into the eCRF at the ET Visit

At the early termination visit, the investigator should transcribe the following data from the day before visit into the eCRF:

- ICR
- ISF
- DIA
- LY900014 dose

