1.3. Schedule of Activities (SoA)

	Screen	Lead in Period -11 to -1	Treatment Period												Safety Follow-up	ET
			Titration Period Days 0 to 35											Maintenance Days 36 to 46		
Day	-21 to -12	-11	0	3	7	10	14	17	21	24	28	31	35	46	53	ET
Visit Window (days)	0	+/-3	+3	-1/+2	-1/+2	-1/+2	-1/+2	-1/+2	-1/+2	-1/+2	-1/+2	-1/+2	-1/+2	+3	+/-3	
Visit	1	2	3	4	5	6	7	8	9	10	11	12	13	14	801	ET
Telephone visits are indicated by shaded columns. Telephone visits can become office visits. Site documentation will serve as the source for telephone visits.																
Informed Consent Signed	X															
Participant eligibility review	X	X														
IWRS	X	X	X	X	X	X	X	X	X	X	X	X	X	X	X	
Clinical Assessments																
Participant demographics	X															
Medical history and preexisting conditions	X															
Physical exam. /height	X															
Body Weight	X		X				X				X			X		X
Note: Participants should be advised to remove their shoes/coats and empty their pockets before the body weight is obtained.																

	Screen	Lead in Period -11 to -1	Treatment Period												Safety Follow-up	ET
			Titration Period Days 0 to 35											Maintenance Days 36 to 46		
Day	-21 to -12	-11	0	3	7	10	14	17	21	24	28	31	35	46	53	ET
Visit Window (days)	0	+/-3	+3	-1/+2	-1/+2	-1/+2	-1/+2	-1/+2	-1/+2	-1/+2	-1/+2	-1/+2	-1/+2	+3	+/-3	
Visit	1	2	3	4	5	6	7	8	9	10	11	12	13	14	801	ET
Vital signs blood pressure and heart rate	X		X				X				X			X		X
	Note: Vital sign measurements should be determined after participants have been seated quietly for at least 5 minutes in a chair with feet on the floor. The arm used for blood pressure measurement should be supported at heart level															
ECG (12-lead, local)	X															
	Participants must be supine for approximately 5 to 10 minutes before ECG collection and remain supine, but awake, during ECG collection.															
Concomitant medications	X	X	X	X	X	X	X	X	X	X	X	X	X	X	X	X
Adverse events and product complaints	X	X	X	X	X	X	X	X	X	X	X	X	X	X	X	X

	Screen	Lead in Period -11 to -1	Treatment Period												Safety Follow-up	ET
			Titration Period Days 0 to 35											Maintenance Days 36 to 46		
Day	-21 to -12	-11	0	3	7	10	14	17	21	24	28	31	35	46	53	ET
Visit Window (days)	0	+/-3	+3	-1/+2	-1/+2	-1/+2	-1/+2	-1/+2	-1/+2	-1/+2	-1/+2	-1/+2	-1/+2	+3	+/-3	
Visit	1	2	3	4	5	6	7	8	9	10	11	12	13	14	801	ET
Participant Education and Management																
Diabetes education and nutrition counseling		X														

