6.9.2. Other Secondary Efficacy Analyses

The analyses described in Section 6.9.2 will include data collected from the Treated Population. Details for the CGM analyses are described in Section 6.13. Continuous secondary efficacy variables, as well as the change from baseline for these variables, will be analyzed by the MMRM or ANCOVA model as described in Section 6.1.

The ICR data from the day before a scheduled visit will be transcribed in eCRF at Visit 2, Visit 3 through Visit 14 and ET Visit, respectively. Any changes and associated to meals for ICR during the Treatment period will be captured. A listing will be provided to include ICR data collected at Visit 2, changes in ICR by meal captured during Treatment period in the eCRF. An MMRM model similar to that for the primary endpoint will be used to analyze actual and change from baseline in ICR.

For the following secondary efficacy endpoints data collected for Visit 3 (baseline) and Visit 14 (endpoint), an ANCOVA model as described in Section 6.1 will be used:

- actual and change from baseline in insulin doses, including mean total daily basal (U/day, U/kg/day), mean total daily bolus (U/day, U/kg/day), and mean total daily insulin dose (U/day, U/kg/day) and mean total daily bolus / total daily insulin dose ratios (%)

The investigator will transcribe the Humalog dose at Visit 3 (data from Day -10 to Day -1) and LY900014 dose at Visit 14 (data from Day 36 to Day 45) to eCRF. To assess the insulin doses over the course of 10 days for each visit, the mean total daily basal dose will be derived based on CGM data collected during lead in period (data from Day -10 to Day -1) and maintenance period (data from Day 36 to Day 45), and mean total bolus doses will be derived based upon the eCRF data collected at Visit 3 and Visit 14.

Relationships between ICR and TDD will be evaluated through regression lines (ICR versus 1/TDD) and compared with the “500 Rule,” which is currently used in clinical practice where

ICR = 500/TDD (Section 2.1 in study protocol) by visit. Regression lines with and without intercept will be analyzed. The analyses will be conducted based upon ICR and mean total daily insulin dose (U/day) collected for Visit 3 and Visit 14, separately.

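### Maintenance insulin doses are fixed to Days 36 to 45, but the last titration visit may fall on Day 36 or 37, so one or two of the ten averaged days can fall on or before it

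*Protocol*

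**What the plan says.** **When settings may change.** Protocol Section 4.1.1 lets the investigator adjust degludec, ICR, ISF and DIA "at any time from Visit 3 (Day 0) to Visit 13 (Day 35"). The Schedule of Activities (Section 1.3) marks dose adjustment at every visit from 3 to 13. It gives Visit 13 a window of -1/+2 days and Visit 14 (Day 46) a window of +3.

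**Which days supply the dose data.** These are calendar days. The bolus data are "the LY900014 dose at Visit 14 (data from Day 36 to Day 45"), and participants must enter degludec doses and main-meal times in the CGM app over the same ten days. SAP Section 6.9.2 derives mean basal dose from the "maintenance period (data from Day 36 to Day 45") and mean bolus dose from the eCRF. A footnote to SAP Table ITSZ.6.2 repeats the fixed days.

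**What the maintenance period is.** Protocol Section 4.1.1 defines it by day in its heading, "Maintenance Period, Day 36 to Day 46", and by visit in its text: "The maintenance period starts following Visit 13". The Schedule of Activities column reads "Maintenance Days 36 to 46", while Sections 4.3.2 and 4.3.3 run maintenance from Visit 13 to Visit 14. For CGM, "Continuous glucose monitoring data collected during the maintenance period will be used as endpoint CGM data". The SAP refers only to CGM data for Visit 14, with no day limits, and its list of analysis periods in Section 6.1 has no separate maintenance period.

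**The concern.** The secondary endpoints ICR×TDD and prandial:TDD ratio are meant to describe the regimen reached at the end of titration. ICR comes from the day before Visit 14, so it reflects the settings then in force. TDD is a ten-day average whose start does not move with Visit 13. When Visit 13 is late but within its window, the average takes in dosing under settings that were then changed at that visit.

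This bears on the question in Protocol Section 9.1: whether a more aggressive ICR than the 500 Rule is needed. If ICR was lowered at a late Visit 13, the lower ICR is multiplied by a TDD that is slightly too small. The product then falls below its settled value, in the direction of the study's own hypothesis. Taking more participants would not average this away.

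**Working it through.** **1. The plan's own figures.** Days 36 to 45 inclusive are 45 - 36 + 1 = 10 days, which matches the 10 days in SAP Section 6.9.2. Days 36 to 46 are 11 days, the stated length of maintenance. Both assume Visit 13 on Day 35.

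**2. Permitted dates (Section 1.3).** Visit 13: 35 - 1 = 34 to 35 + 2 = 37. Visit 14: 46 to 46 + 3 = 49.

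**3. Overlap.** Let k be the number of days in 36 to 45 that fall on or before Visit 13, counting study days from Day 0 with no reset.

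| Visit 13 on Day | k of 10 | Wholly before the visit | Days strictly between Visits 13 and 14 (Visit 14 on Day 46 / Day 49) |
|---|---|---|---|
| 34 | 0 | none | 11 / 14 |
| 35 | 0 | none | 10 / 13 |
| 36 | 1 | none (visit day only) | 9 / 12 |
| 37 | 2 | Day 36 | 8 / 11 |

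No protocol deviation is needed for k = 1 or k = 2.

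**4. Effect on TDD.** Let p be the prandial share of TDD after the change and s the relative cut in ICR at Visit 13. Carbohydrate intake and basal dose are held constant, and all prandial insulin is taken to scale with 1/ICR. A pre-change day then has a prandial dose of (1 - s) times the later one, and a TDD of (1 - p·s) times the later one. So

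observed TDD / settled TDD = 1 - (k/10)·p·s.

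I assume p = 0.5; Protocol Section 2.1 reports bolus:basal near 50:50 in the earlier Phase 3 trials. I also assume s of 10 to 20%, which the documents do not give.

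| k | s = 10% | s = 20% |
|---|---|---|
| 1 | 0.1 × 0.5 × 0.10 = 0.5% too low | 0.1 × 0.5 × 0.20 = 1.0% too low |
| 2 | 0.2 × 0.5 × 0.10 = 1.0% too low | 0.2 × 0.5 × 0.20 = 2.0% too low |

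**5. Effect on the endpoints.** ICR is the final value, so ICR×TDD falls by the same percentage. A settled product of 500 would be computed as 500 × 0.99 = 495 or 500 × 0.98 = 490 with k = 2. The ratio of mean bolus to mean TDD becomes p(1 - ks/10)/(1 - kps/10). With k = 2 that is 0.49/0.99 = 0.495 for s = 10% and 0.48/0.98 = 0.490 for s = 20%, against 0.500, so it is 0.5 to 1.0 percentage points low. If ICR was raised instead, the signs reverse.

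**6. Group level.** If a fraction f of participants have such a visit and such a change, the mean relative shift is f times these figures. The documents give no distribution of Visit 13 dates, so f could be anything from 0 to 1.

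**The case against.** The case for leaving the plan alone has four parts.

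- **The overlap depends on day counting.** It needs study days counted from Day 0 with no reset at Visit 13. The documents do not say which applies. This stands, and it makes the finding conditional.
- **The size is a worst case.** The visit day is counted in full, the ICR step is assumed and must come at the last titration visit, and correction boluses depend on ISF rather than ICR. This stands too. Without the visit day, a Day 37 visit has k = 1 and the shift is 0.5 to 1%.
- **The pairing problem is wider than the window.** Safety changes are allowed during maintenance, so ICR on the last day can differ from the averaged regimen under any window. That is correct, and the fix does not remove it.
- **A uniform ten-day window is defensible.** It gives every participant the same number of days and a bounded workload. That is a fair reason to prefer the smaller of the two fixes, but not to average in days known to precede the last titration visit.

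A reader might go further and infer that time in range, the primary endpoint, is contaminated in the same way. The documents do not support that: CGM is nowhere limited to Days 36 to 45, and under the visit-based definition no glucose data from before Visit 13 enter.

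A reader might also extend the point to the lead-in, since Visit 2 may be as late as Day -8 while data are requested from Day -10. Days before Visit 2 hold no study CGM or InPen data, so they are empty rather than wrong. A gap in logging before a postponed Visit 3 would arise only if Day 0 did not move with that visit, and Section 4.1.1 labels Visit 3 as Day 0.

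**Conclusion.** The point holds for the insulin dose data. With Visit 13 on Day 36 or 37, and days counted from Day 0, 1 or 2 of the 10 averaged days fall on or before the last titration visit. This reaches ICR×TDD, the prandial:TDD ratio and the regressions that use TDD; ICR at the end of maintenance is unaffected. For a Day 37 visit the error is about 1 to 2% of TDD under the stated assumptions, in an unknown share of participants. It is small but systematic wherever the last changes go mostly one way.

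For CGM, what remains is two definitions of one period that disagree whenever Visit 13 does not fall on Day 35. On the visit-based definition, a Visit 14 after Day 46 also adds CGM days for which no dose or meal entry is required. The definitions should be reconciled so that the primary endpoint's window is not left to programming. No bias in the primary endpoint has been shown, and the sample size statement is untouched.

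**What to change.** **Full version.** In the Schedule of Activities (Section 1.3), Protocol Section 4.1.1 and SAP Sections 6.1, 6.9.2 and 6.13, define one endpoint window for CGM, meal, degludec and bolus data: the day after actual Visit 13 to the day before actual Visit 14.

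**Minimum version.** Keep Days 36 to 45 for doses, exclude any day on or before actual Visit 13 from the average, and state which definition of the maintenance period governs CGM.

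**Cost.** Both are wording changes that use visit dates already recorded, with no added visit or procedure. The window then varies by participant: 8 to 14 days under the full version, 8 to 10 under the minimum. The full version can add up to 14 - 10 = 4 days of logging and of transcribing individual doses. The minimum version adds none, but averages over 8 or 9 days for some participants.
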